8. HSAT

The home sleep study will be done using the WatchPAT HSAT device (Itamar Medical). The WatchPAT (see Figure) is non-invasive, FDA-approved, has extensive validation, easy to use, with a low rate of study failure.²⁴ The device monitors peripheral arterial tone as an index of sympathetic activity changes, pulse oximetry, actigraphy, sleep

position and snoring. The WatchPAT report includes the AHI (events with 4% desaturation), Respiratory Disturbance Index (RDI) which includes respiratory events associated with 4% desaturations or arousals, ODI, sleep staging identification, snoring level and body position. Data from the WatchPAT will be reviewed for artifacts. Subjects will be instructed on its use at home, shown a video for proper use (<https://www.youtube.com/watch?v=VhFd88QM0lo>), and provided written instructions.

9. Wave mattress support

The Hill-Rom Early Innovation team has developed a device ("Wave 4.3"), an articulating mattress support intended to treat POSA.

As above, the investigational device is an NSR device that follows the abbreviated Investigational Device Exemptions (IDE) requirements at 21 CFR 812.2(b) addressing labeling, IRB approval, informed consent, monitoring, records, reports, and prohibition against promotion for an NSR device study.

The Wave 4.3 mattress support is an insert, placed underneath the user's existing mattress, that when inflated increases the longitudinal incline of the mattress support, increasing in inclination in the direction of the head of the bed. The resulting mattress contours are such that the mattress has a lateral inclination of approximately 15 degrees in the head section and 10 degrees in the torso section. In addition to the features allowing the user to activate and deactivate creation of this Graduated Lateral Rotation™ orientation, this device has sensors and monitoring system allowing for remotely monitoring the status of the system, including confirming that the supports are achieving the prescribed support angles, and that the system is working as planned.

The Wave 4.3 mattress support has been designed and prototyped by Hill-Rom, using a number of components from its commercial medical bed mattresses, including the air bladders, air supply system. A detailed design of the device is attached. The device will be delivered and installed by Hill-Rom personnel in the presence of the research coordinator who will instruct the subject on its use.

IV. Data Analysis

Sample size

The primary endpoint for the study is the change in the AHI from baseline to the 14th night of sleeping with the surface. From prior data, we estimate the standard deviation of the paired differences to be 11.4. Using a one-sided paired t-test with type I error rate of 0.05, we will have 80% power to detect a 6 point reduction in AHI with 24 evaluable patients. We assume a loss to follow-up rate of 20% and a screen failure rate of another 20%; thus will enroll 40 patients.

Statistical methods

The primary analysis will assess the change in AHI from baseline to the 14th night of sleeping on the surface. We will use a one-sided paired t-test to assess the reduction in AHI. If the study is not stopped early for either efficacy or futility, the final analysis will conclude a significant reduction in AHI if the p-value is less than 0.048. Secondary endpoints will be assessed similarly using paired t-tests or appropriate non-parametric tests for paired data. We may also explore longitudinal changes in actigraphy measures using mixed effects models.

Interim Analysis:

Interim analyses for efficacy and non-binding futility will be conducted when 50% of the evaluable patients have reached the primary endpoint after 14 days of using the device. That is, it will be conducted after 12 patients have an evaluable primary endpoint. The analysis will assess the primary endpoint using the error spending approach described by Lan and Demets.^{25,27} The study will be stopped early for efficacy if the p-value is less than 0.006 and stopped for futility if the p-value is greater than 0.37. If neither boundary is reached, the trial will not be stopped early and will enroll the full planned number of participants.

V. Event Reporting

(a) Adverse Events

The ICH Guideline for Good Clinical Practice E6(R1) defines an adverse event (AE) as:

Any untoward medical occurrence in a patient or clinical investigation subject administered a pharmaceutical product and which does not necessarily have a causal relationship with this treatment. An AE can therefore be any unfavorable and unintended sign (including an abnormal laboratory finding), symptom, or disease temporally associated with the use of a medicinal product, whether or not considered related to the medicinal product.

As this is a study that does not include a pharmaceutical product intervention, this definition would include AEs that occur as a result of protocol procedures and protocol treatment.

A serious adverse event (SAE) is any AE that:

- Results in death
- Is immediately life-threatening
This term refers to an event in which the subject was at risk of death at the time of the event; it does not refer to an event that may have led to death.
- Requires inpatient hospitalization or prolongation of existing hospitalization
In general, hospitalization signifies that the subject has been detained (usually involving at least an overnight stay) at the hospital or emergency ward for observation and/or treatment that would not have been appropriate in an outpatient setting.
- Results in persistent or significant disability/incapacity
The term disability means a substantial disruption of a person's ability to conduct normal life functions.
- Is an important medical event that may jeopardize the subject or may require medical intervention to prevent one of the outcomes listed above.

Medical or scientific judgment should be exercised in deciding whether expedited reporting is appropriate in this situation. Examples of medically important events are intensive treatment in an emergency room or at home for allergic bronchospasm, blood dyscrasias, or convulsions that do not result in hospitalizations; or development of drug dependency or drug abuse.

1. Collecting and reporting adverse events:

All AEs occurring after subject has signed consent and up to the study completion visit must be recorded on specific data collection forms.

2. Collecting and reporting Serious Adverse Events:

The OSU Event Reporting Form should be used to report untoward events that may affect participants in research approved by an OSU IRB. Events requiring prompt reporting include adverse events, protocol deviations, and other unforeseen problems or findings that suggest participants, research staff, or others are placed at greater risk by the research than previously expected. These events, classified broadly as unanticipated problems involving risks to participants or others, must be reported promptly to the

IRB. Unanticipated problems can occur in any type of research and may involve physical, psychological, social, legal, or economic harms.

Events Requiring Prompt Reporting

Events that may represent unanticipated problems involving risks to participants or others and therefore require prompt reporting include the following:

- Adverse events or injuries that are serious, unexpected, and related;
- Events requiring prompt reporting according to the protocol or sponsor;
- Reports, interim analyses, or other oversight committee/monitoring reports altering the risk/benefit profile;

These events should be promptly reported (see below), regardless of whether they occur during the study, after study completion, or to a participant who has withdrawn from or completed study participation.

Timeframe for Reporting

All internal events (those occurring in research at OSU or at a site under an OSU IRB's jurisdiction) as described above should be reported **within 10 days** of the Investigator's or research staff member's learning of the event. Events resulting in temporary or permanent interruption of study activities by the Investigator or sponsor to avoid potential harm to participants should be reported **immediately (within 48 hours)** whenever possible.

Additional Information

Related adverse events and other problems involving risk that do not meet the reporting requirements and do not represent potential unanticipated problems involving risks to participants or others should be reported in summary form at the time of continuing IRB review. However, any problem or adverse event that an investigator believes could influence the safe conduct of the research should be reported promptly.

(b) Protocol Deviations

Protocol deviations are accidental or unintentional changes to the protocol or procedures. In the event that the protocol deviation involves risk to the subject or potential risk to future participants, or with the potential to recur or significantly impacts the integrity of the research data, the event should be reported to the IRB in a timely manner, in accordance with their reporting guidelines.

VI. Ethical Considerations

The study will be conducted in accordance with the ICH guidelines on GCP, the GCPs applicable to any region where the study is conducted, and the ethical principles set forth in the Declaration of Helsinki. Good clinical practice is defined as a standard for the design, conduct, performance, recording, analysis, and reporting of clinical studies in a way that provides assurance that the data and reported results are credible and accurate, and that the rights, safety, and well-being of study participants are protected.

Per GCP, the protocol will be reviewed and approved by the IRB or IEC of each participating center prior to study initiation. The investigator will keep the IRB/IEC informed as to the progress of the study.

(a) Consent procedures

The investigator/study personnel will explain the nature of the study, and will be available to answer questions regarding procedures, risks and alternatives to participation. The consenter will inform the subject that participation is voluntary and that the subject can withdraw or be withdrawn from the study at any time. The principal investigator or his/her entitled designee will obtain written informed consent from each subject. Documentation of the informed consent process along with the original consent form will be maintained in the subject's research folder. A copy of the signed informed consent will be provided to the subject for their records.

(b) Subject compensation

Participants who qualify for the study will receive up to \$400 compensation for participating in the study in the form of a ClinCard or by direct deposit (optional for OSU employees who may elect to receive payment by check). They will receive \$200 at Visit 3 and \$200 after Visit 4. If the participant is unable to complete all the visits, compensation will be prorated for the visits that are completed. All subject payments are taxable income.

VII. Data Handling and Record Keeping

The investigator shall maintain the records of the study e.g.: subject research charts, regulatory documents and all other study specific documentation for a minimum of 15 years or in accordance with currently OSU-IRB regulations.

1. Confidentiality

- Confidentiality of all records will be maintained and data will be kept in a locked filing cabinet and only research staff and authorized members of the IRB will have access.
- Electronic data is protected by codes to which only research staff and authorized members of the IRB, Office of Responsible Research Practices, and Data Safety Monitoring Committee will have access
- The PHI to be collected; who will use the information within the institution and why; who may disclose the information and to whom; the subjects rights to access research information and their right to withdraw authorization (approval) for any future use of personal health information are all listed in the HIPAA form specific to the research
- The names of subjects and any other identifying information will be kept in a secure location.
- Should publications result from this study all PHI will be removed.

2. Research and/or Development Agreement with Hill-Rom

This research will be performed under a fully executed agreement between The Ohio State University and Hill-Rom (see attachment).

VIII. Data Safety Monitoring Plan

The risks involved with sleeping with the Wave mattress support, completion of questionnaires, HSAT, and actigraphy are minimal.

This study will be monitored to ensure participant safety and data integrity. The monitoring for this study will be conducted by the Principal Investigator and the study team. The information that will be evaluated will be the incidence and severity of adverse reactions related to the study procedures, enrollment and efficiency of data capturing. The adverse events will be assessed on a case by case basis at the time the study team is aware of the event.

Overall study monitoring will take place on an ongoing basis with study review meetings taking place at least every 4 months. In the event the side effects suggest the risk outweighs the benefit, the study will be stopped and the IRB notified in order to evaluate possible solutions to the risk problem.

VI. Bibliography

2. Strollo PJ, Jr., Rogers RM. Obstructive sleep apnea. *N Engl J Med* 1996;334:99-104.
3. Flemons WW. Clinical practice. Obstructive sleep apnea. *N Engl J Med* 2002;347:498-504.
5. Kuna ST, Gurubhagavatula I, Maislin G, et al. Noninferiority of functional outcome in ambulatory management of obstructive sleep apnea. *Am J Respir Crit Care Med*;183:1238-44.
8. George CF. Reduction in motor vehicle collisions following treatment of sleep apnoea with nasal CPAP. *Thorax* 2001;56:508-12.
10. Somers VK. Sleep--a new cardiovascular frontier. *N Engl J Med* 2005;353:2070-3.

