- This will occur on the 14th day of sleeping with the mattress support (that is, after night 13). The purpose of this visit is to provide the HSAT device to be used while sleeping with the mattress support.
- Medication changes
- **Expected visit length: 20 minutes**

Visit 4.

- Return HSAT equipment.
- The following will be obtained during this visit:
 - a. ESS
 - b. FOSQ
 - c. Assessment of sleep quality: VAS and Questionnaire
 - d. Medication changes
- **Expected visit length: 30 minutes**
- It may be necessary to repeat the home sleep study for another night if data after sleeping with the Wave mattress support is not adequate.

Phone Calls: Phone calls will be made by an investigator or research staff to answer any questions that participants may have (will occur between Visits 2 and 3): after the second night (third day) and seventh night of sleeping on the Wave 4.3 surface.

Mattress support pick-up: The mattress support will be picked up by professional staff of the sponsor (Hill-Rom) in the presence of the research coordinator or investigator at a mutually agreed time.

Visit Schedule

Procedures	Visit #			
	1	2	3	4
Screening consent		x		
Study consent			x	
Pregnancy test, if applicable		x		
Clinical Sleep Study Results*	x			
CPAP adherence, if applicable	x			
Sleep Questionnaire and Medical History	x			
Medication list	x			
Medication changes		x	x	x
Height and weight	x			
Neck Circumference	x			
BP, Pulse rate, SpO ₂	x			
Provide HSAT Equipment	x	x		
ESS	x		x	
FOSQ	x	x		

Sleep quality	X	X
Wave instructions	X	
Actigraphy**	X	X X
Sleep diary**	X	X X

BP= blood pressure

SpO₂= oxygen saturation by pulse oximetry

HSAT= home sleep apnea test

ESS= Epworth Sleepiness Scale

FOSQ= Functional Outcomes of Sleep Questionnaire

VAS= Visual Analog Scale

*Clinical sleep study is completed per standard clinical care.

** Done while sleeping with Wave Mattress support for 14 days

D. Detailed Procedures

1. Clinical Sleep Study:

Subjects will undergo diagnostic sleep study according to the evaluation of their physician. This is the sleep study performed within the context of usual clinical care that will determine whether subjects meet the criteria for POSA.

2. OSU Sleep Questionnaire and Medical History (15 minutes)

Sleep Questionnaire (Visit 1 only; No need to complete if previously completed the OSU Sleep Disorders Center Questionnaire in sleep clinic)

3. Medication List (5 minutes)

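### Does the missing definition of an evaluable home sleep test undermine the primary test of AHI?

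*Combined protocol and SAP*

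**What the plan says.** Section IV, Sample size, sets the endpoint: "The primary endpoint for the study is the change in the AHI from baseline to the 14th night of sleeping with the surface". It then says that "we will have 80% power to detect a 6 point reduction in AHI with 24 evaluable patients", and on enrolment: "We assume a loss to follow-up rate of 20% and a screen failure rate of another 20%; thus will enroll 40 patients". Under Interim Analysis, the timing of the look is that "it will be conducted after 12 patients have an evaluable primary endpoint". The same paragraph describes the primary endpoint as reached once 14 days of device use are complete.

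The HSAT is handed out at Visit 3. Of that visit the Study Plan says: "This will occur on the 14th day of sleeping with the mattress support (that is, after night 13". The first on-Wave recording is therefore night 14. Under Visit 4, it "may be necessary to repeat the home sleep study for another night if data after sleeping with the Wave mattress support is not adequate". The Visit 1 procedures give a similar repeat for a technically inadequate baseline recording.

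The HSAT paragraph under Detailed Procedures says: "Data from the WatchPAT will be reviewed for artifacts". It lists the AHI among the items in the device report and describes the device as having few failed studies. The Wave paragraph mentions "the features allowing the user to activate and deactivate creation of this" lateral tilt, together with sensors that can track the system's status.

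No section defines *evaluable* or *adequate*, sets a window or limit for repeats, or mentions support-off nights in the analysis.

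**The concern.** The word *evaluable* decides which readings enter the final test and which 12 patients make up the interim look. Three questions have no written answer: what makes a recording adequate, whether a repeat on night 15 or later can stand for the night-14 endpoint, and whether a night with the support off counts.

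The study has no control arm, and the investigator and study team do the monitoring. Nothing requires adequacy to be judged before the AHI is seen. If unfavourable readings were more readily called inadequate, the one-sided error would exceed its planned level. With 24 readings, a single one can move a near-threshold result across 0.048. The plan also assumes 20% loss without saying how the losses will be described.

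**Working it through.** **Inputs from section IV.** SD of paired differences 11.4; reduction 6; n = 24; one-sided paired t-test; final threshold p < 0.048; interim at 12 with efficacy threshold p < 0.006.

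**The plan's own figure.** Noncentrality = (6/11.4) × √24 = 2.58 on 23 degrees of freedom. Exact power is 80.4% at 0.05 and 79.8% at 0.048, so the stated 80% reproduces. The smallest significant mean fall at 0.048 is 1.736 × 11.4/√24 = 4.04.

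**What the text implies on each open question.**

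- *Repeat.* Another night is allowed only when the data are not adequate. The repeat therefore replaces an unusable recording and is not a second attempt after a usable one. A reading on night 15 also fits the interim paragraph's description of an endpoint reached after 14 days of use.
- *Support off.* The endpoint concerns sleeping on the surface, and no passage excludes a night because the tilt was inactive. The default is to count it.
- *Adequacy.* No criterion is given. The test needs only that the judgement does not depend on the change in AHI.

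**Error if readings are lost for reasons unrelated to the AHI.** Simulated with no true effect and one, two or three of 24 readings dropped at random, the final test rejects in about 4.8% of trials each time. Power at a true fall of 6 goes from 79.8% to 78.2%, 76.5% and 74.6% with 23, 22 and 21 readings.

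**Error if choices do depend on the AHI (assumed behaviour).** One, two or three readings are fixed in advance as borderline, and each is dropped only if its AHI rose. There is no true effect.

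| Borderline readings | Final test alone | With the interim look |
|---|---|---|
| 0 | 4.8% | 5.0% |
| 1 | 5.6% | 6.0% |
| 2 | 6.6% | 7.0% |
| 3 | 7.7% | 8.1% |

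If three such readings are instead repeated and the second used, the final-test error is 5.6% to 6.7%, for correlations of 0.7 down to 0.3 between the two changes.

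**Support-off nights (assumed zero mean change, SD 11.4; other nights fall by 6).**

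| Off nights of 24 | Power, all counted | Power, off nights excluded | Rules disagree |
|---|---|---|---|
| 1 | 76% | 78% | 5.7% |
| 2 | 73% | 76% | 8.8% |
| 3 | 69% | 75% | 11.7% |

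If off-night changes have SD 6 instead, the rules disagree in 2.9%, 4.4% and 5.8% of trials. Neither rule inflates the error if it is applied without regard to the AHI.

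**Losses.** The plan's arithmetic is 40 − 8 − 8 = 24, which gives 32 users with 8 lost. If completers fall by 6.0 and the 8 lost have zero change, the all-users fall is 6.0 × 24/32 = 4.5. For significance to disappear, the 8 would need a mean change of about −3.5, that is, a worsening. At that value the all-users mean is (24 × 6 − 8 × 3.48)/32 = 3.63 and the combined SD is about 11.96. The threshold is then 1.717 × 11.96/√32 = 3.63.

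**The case for a change.** The strongest case for a change is that this is a formal test with stopping boundaries, and its error rates hold only if the inputs are settled independently of the results. A repeat provision without a criterion permits discretion. At the extreme, if the single least favourable of 24 readings were set aside with the AHI known, the one-sided error of the final test would be 12.0%; with two it would be 21.8%, and with three 33.2%. One reading can also decide a close result. With n = 24, mean fall 3.5 and SD 11.4, p = 0.073. Removing one reading with a rise of 11.4 leaves n = 23, mean (24 × 3.5 + 11.4)/23 = 4.15 and SD 11.2, so p = 0.045.

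It stands that the criterion, the repeat window and the handling of support-off nights are unwritten, and that nothing prevents the adequacy reader from seeing the AHI. The consequences are weaker than they look. That the reader does see the AHI is an inference, since no passage says who judges adequacy or what they are shown. The 12% figure is a bound under deliberate selection of the worst reading, not a prediction. Three problem recordings of 24 fit poorly with the low failure rate the protocol cites. The near-threshold example was constructed, and any 24-patient test has such datasets even under a perfect rule.

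Writing rules down would also deliver less than it promises. The documents supply no recording threshold or last acceptable night to write in. A reader kept from the AHI may need extra staff, because the AHI is in the device report. A rule added at the interim would come too late to protect the first 12 readings. A tipping-point analysis and a disposition table are matters of preference in a preliminary single-arm feasibility study.

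**Conclusion.** No change follows. The plan leaves out detail, but followed as written it gives a valid paired test: the night-14 reading, a replacement only when that reading is unusable, and no exclusion of support-off nights. Its 80% power is correct. Error rises only if readings are discarded because the AHI rose, by about 0.8 percentage points for one reading and 2.9 for three on the final test, and the documents do not indicate that this would be done. The handling of support-off nights affects power by about 2 to 6 points for one to three such nights at SD 11.4, and less at SD 6. The result describes patients who completed night 14. On the plan's own loss figures, with completers at the planned 6-point fall, the patients lost would have to worsen by about 3.5 points on average before significance disappeared.

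This rests on two assumptions: that the study team applies the repeat provision on technical grounds, and that few recordings are affected. Numbers of inadequate recordings or support-off nights are not in the documents; one to three of 24 is the range examined.

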- Patients who meet the above criteria who have been prescribed CPAP or dental device but are adherent to treatment will be enrolled in the study provided that: a) they are willing to use the Wave device instead of their CPAP or dental device for the duration of the study, and b) they do not have severe OSA defined as an AHI > 30 events/hr in their clinical sleep study.

B. Key Exclusion Criteria

- Incapable of giving informed consent
- Under the age of 18
- Active titration of medication
- Pregnancy, lactation (will be screened with urine pregnancy test)
- Self-reported Substance abuse (current)
- Excessive alcohol consumption
 - Excessive alcohol use is defined as:
 - More than 3 glasses of wine a day
 - More than 3 beers a day
 - More than 60 mL of hard liquor a day
- Use of home oxygen
- Presence of severe daytime sleepiness defined as an Epworth sleepiness scale score ≥ 16 or a prior history of falling asleep while driving
- Presence of cardiac pacemaker or automatic implantable cardioverter-defibrillator (AICD).
- Unstable medical problem such as uncontrolled hypertension.
- Body Mass Index (BMI) $>45 \text{ kg/m}^2$
- Any other clinically significant condition that, in the opinion of the investigators, might put the subject at risk of harm during the study or might adversely affect the interpretation of the study data.

2. Screening Procedures

A screening visit will be scheduled to determine eligibility. A separate informed consent for the purpose of screening potential candidates will be obtained. Female patients of childbearing potential will be required to have a negative pregnancy test result at screening.

After their study participation has ended, those with an AHI ≥ 5 /hour based on the HSAT will be referred to their primary care physician or the sleep medicine clinic for treatment discussion using established therapies

3. Vulnerable Populations

- Children, fetuses, neonates, or prisoners are not included in this research study.

4. Populations vulnerable to undue influence or coercion

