Cognitively impaired persons are not included in this research study, since the potential subject has to be able to give informed consent. Should an OSU employee or student be approached, they will be given the opportunity and time to consider participation and will be reassured that declining to participate will not jeopardize or hinder their standard of care at the OSU Sleep Disorders Center, nor will it have any bearing on either their student status or employment.

5. *Inclusion of Women and Minorities*

Both men and women of all races and ethnic groups are eligible for this study.

C. Study Plan

This is a preliminary single-arm study. The study will last up to 4 weeks including the screening period. Subjects will sleep using the mattress support at home for two consecutive weeks.

Outcome measures will include: AHI derived from HSAT (primary outcome), oxygen desaturation index (ODI), Epworth Sleepiness Scale (ESS) score, Functional Outcomes of Sleep Questionnaire (FOSQ), Visual Analog Scale (VAS) and questionnaire assessments of sleep quality, and actigraphic sleep measures. Subjects will also keep a sleep diary every night for the duration of the study. Subjects will be asked about their bed partners' report on snoring and witnessed apneas.

Visit 1: Screening Visit and Procedures

A separate informed consent for the purpose of screening potential candidates will be obtained.

Instead of an in-person visit, the participant consent for the purpose of screening will be conducted using a REDCap-based electronic consent form for those who are willing and able to do this. The consent form will be developed in REDCap, a secure, web-based, HIPAA-compliant, data collection platform with a user management system allowing project owners to grant and control varying levels of access to data collection instruments and data (e.g. read only, de-identified-only data views) for other users. Potential participants will participate in the consent process by:

- Being approached in-person at The Ohio State University and accessing the REDCap survey via iPad or other portable electronic device and/or
- Self-initiated access of consent forms on personal portable electronic devices using posted QR codes or web-links on study posters, brochures, or websites. Self-initiated accessing of consent forms may occur at The Ohio State University campus or at home.

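### Do the secondary endpoints need a stated sidedness, significance level and interval so that worsening is formally covered?

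*Combined protocol and SAP*

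**What the plan says.** Section IV, under Sample size and Statistical methods, specifies the primary endpoint closely. The design calculation is stated as "Using a one-sided paired t-test with type I error rate of 0.05", and the analysis as "We will use a one-sided paired t-test to assess the reduction in AHI", with a final threshold of 0.048. The Interim Analysis paragraph adds boundaries at 12 evaluable patients: "The study will be stopped early for efficacy if the p-value is less than 0.006", and a non-binding futility limit of 0.37. That paragraph concerns the primary endpoint only.

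The secondary endpoints then get one sentence: "Secondary endpoints will be assessed similarly using paired t-tests or appropriate non-parametric tests for paired data". No section gives them a sidedness, a significance level or an interval. Actigraphy is mentioned separately, as a possible exploration: "We may also explore longitudinal changes in actigraphy measures using mixed effects models".

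Two other places bear on the reading. Section I words objectives 2 and 3 as determining the effects of the device on sleepiness, daytime function and sleep quality, with no direction. Section III.C describes the design: "This is a preliminary single-arm study".

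**The concern.** The word *similarly* comes straight after a one-sided test and its threshold, so the natural sequential reading is that ESS, FOSQ, sleep quality and ODI are also tested for benefit only. Such a test has no rejection region for worsening. On the other reading the tests are two-sided. The plan does not choose, so the choice could be made after the data are seen.

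Worsening is conceivable. The inclusion criteria admit patients who adhere to CPAP or a dental device, provided that "they are willing to use the Wave device instead of their CPAP or dental device for the duration of the study". Section III.D.9 describes a sleeping surface with a lateral tilt of about 15 degrees at the head and 10 degrees at the torso, which might disturb sleep. If these outcomes deteriorated, no test or interval stated in advance would say so. The choice of tail could also decide whether a benefit is reported as significant.

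**Working it through.** **Inputs from Section IV.** SD of the paired AHI difference 11.4; target reduction 6; 24 evaluable patients; one-sided 0.05; interim at 12 patients; thresholds 0.006 and 0.048.

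**Assumed.** The documents give no SD for any secondary endpoint, so true shifts are set at 0.4, 0.5 and 0.6 SD of the paired difference.

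**Formula.** For a standardised shift d and n pairs, t has n − 1 degrees of freedom and noncentrality d√n. One-sided power is P(t > t(1 − α, n − 1)). Two-sided power uses t(1 − α/2, n − 1) and both tails.

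**1. The plan's own figure.** d = 6/11.4 = 0.526; noncentrality 0.526 × √24 = 2.58; critical value t(0.95, 23) = 1.714. Power is 80.4%, so 24 patients for 80% power reproduces. At the 0.048 threshold the fixed-sample power is 79.8%. Taken as one-sided, boundaries of 0.006 and 0.048 at half information give an overall type I error of 0.0499 (normal approximation). The primary analysis is coherent, and nothing in it depends on the secondaries.

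**2. What the tail costs or buys for a secondary endpoint.**

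| n | True shift (SD) | One-sided 0.05, power for benefit | Two-sided 0.05, power | Difference (points) |
|---|---|---|---|---|
| 24 | 0.4 | 60.1% | 46.7% | 13.4 |
| 24 | 0.5 | 76.8% | 65.0% | 11.7 |
| 24 | 0.6 | 88.6% | 80.4% | 8.2 |
| 12 | 0.5 | 49.2% | 35.3% | 13.9 |

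Differences are taken before rounding. The two-sided column also gives, by symmetry, the chance of declaring a worsening of the same size. For a one-sided benefit test that chance is zero. If 0.048 were carried over instead of 0.05, the one-sided powers at n = 24 would be 59.3%, 76.1% and 88.2%, which is immaterial.

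The n = 12 row applies if the trial stops early for efficacy. At the plan's AHI effect that has a probability of about 17% (one-sided p < 0.006). The row is not conditioned on having stopped, which matters most for ODI because it comes from the same recording as AHI.

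**3. Is evidence of worsening lost under the one-sided reading?** The paired t statistic is the same whichever tail is used. If p₁ is the one-sided p-value for benefit, the two-sided value is 2 × min(p₁, 1 − p₁). So p₁ > 0.975 is the same event as a two-sided p < 0.05 towards worsening. A reader given p₁ and the mean change can recover the two-sided result.

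**4. Can the one-sided reading produce a false claim of benefit when patients worsen?** With a true worsening of 0.526 SD and n = 24, the benefit test rejects with probability about 0.00002.

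**5. Precision available under either reading.** The 95% interval half-width is t(0.975, n − 1)/√n: 2.069/√24 = 0.42 SD at n = 24 and 2.201/√12 = 0.64 SD at n = 12. It follows from the same mean and SD that any paired t-test produces.

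**The case for a change.** The strongest case for a change is that the plan intends formal tests of these outcomes, and exploratory status excuses light multiplicity control but not an undefined test. Objectives 2 and 3 ask about effects in both directions, and for a sleep surface the question whether sleep gets worse is central. With so few patients an interval says more than a p-value, and none is promised. A mean shift in ESS or FOSQ need not appear as an adverse event. The remedy would be two or three sentences and no new data.

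Much of this stands as description. Sidedness, level and interval are unstated, and an analyst could choose the tail late. It does not carry through to a need for change, for four reasons.

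- The benefit-only test is one reading, not what the plan says. The sentence goes on to name paired methods rather than a direction, and the non-directional objectives favour the two-sided reading.
- Where the readings disagree, one says significant benefit and the other says not significant, from the same estimate in the same direction. Neither hides harm or invents it.
- A formal finding of worsening would have little inferential weight. There is no control group, and some of any deterioration could come from patients giving up CPAP or a dental device.
- Imposing two-sided tests has a price: about 12 points of power for a 0.5 SD benefit at n = 24. It also would not make the secondaries confirmatory. Five measures (ODI, ESS, FOSQ, sleep-quality VAS and questionnaire) each tested at 0.05 would have a chance of 1 − 0.95⁵ = 23% of at least one false positive if independent, and the choice between a t-test and a non-parametric test would still be open.

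**Conclusion.** This is missing detail, not an error. Under either reading the secondary analyses give valid paired estimates and lead to no false conclusion, and a competent analyst would report the mean change in whichever direction it falls. The practical difference is whether a moderate benefit earns the label significant: 8 to 13 percentage points over shifts of 0.4 to 0.6 SD at n = 24, and about 14 points at 0.5 SD if the trial stops at 12. Those sizes rest on the assumed shifts, on complete pairs and on t-based tests, because the documents give no SD for these endpoints.

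The AHI test, the 24 evaluable and 40 enrolled patients, and the 0.006, 0.37 and 0.048 thresholds are unaffected. One-sided or two-sided testing of secondaries in a preliminary single-arm feasibility study is a trade-off on which reasonable statisticians differ. No change to the plan is called for.
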